3.1.4 Summary Statistics

Categorical data will generally be summarized with counts and percentages of subjects. The denominator used for the percentage calculation will be clearly defined. Continuous data will generally be summarized with descriptive statistics including n (number of non-missing values), mean, median, standard deviation, interquartile range (Q1, Q3), minimum, and maximum.

3.1.5 Evaluation of Site Effect

Site will be modeled as a random effect to account for variability in the outcome due to the differences between sites. A subgroup analysis for each site will be run.

3.1.6 Handling of Dropouts and Missing Data

For participants who have missing observations on 90-day mRS, 24-hour NIHSS, worsening stroke, or infarct volume, the missing data in the primary analyses will be managed with an assumption of MAR using longitudinal mixed models. In addition, every effort will be made to complete assessments using the participants legally authorized representative (LAR) for information if needed. Assessments with missing elements will be considered missing as a whole. Missing dates will be queried at the site level prior to database lock.

3.1.7 Handling of Death

Subjects who die during the study will be scored as follows for all scheduled visits following the death: 6 for mRS, 42 for NIHSS and 0 for BI. The value 6 for mRS is part of the mRS definition. The values for NIHSS and BI are conventions, consistent with the worst possible score.

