13 ADDENDUM

13.1 COVID-19 Considerations

Minimizing Risk to Participants and Staff

The protocol includes the following adaptations to minimize risk while prioritizing the overall well-being and best interests of all involved in the trial. This protocol was written considering the impact of COVID-19 on trial participants, site staff and sponsor staff. With these priorities in mind, the protocol design will still permit assessment of safety of RNS60.

- **Minimize the number of study visits** to align with the trial endpoints
- **Minimize the number of trial specific activities.** The trial was designed to align with standard of care protocols for acute stroke. For example, obtaining data from standard of care assessments conducted during routine stroke care, for the collection and reporting of some safety outcomes (vital signs, laboratory results) and imaging outcomes.
- **Conduct visits by telemedicine or by telephone** at Day 30 and Day 90, where permitted, when a participant is unable to attend the site physically. This will permit the timely collection of efficacy endpoints (mRS, NIHSS, BI and EQ-5D-5L) and safety data (AE and SAE collection). If the contact is made by phone, only the NIHSS assessment will not be completed, all other assessments will be obtained.
- **Use of remote electronic consent**, where permitted, to obtain initial consent from the LAR, who may not be able to enter the hospital, and to obtain regained capacity consent from participants who did not consent prior to their discharge from hospital.
- **Use of electronic Clinical Outcome Assessments (eCOA)** for the conduct of the mRS, NIHSS, BI and EQ-5D-5L assessments at Day 30, and Day 90 timepoints. This will permit site staff to collect trial endpoints even if they are not permitted into the hospital, reduce data entry time and reduce the time on-site for CRAs in order to monitor the data.

In addition to the above items included in the protocol, ongoing risk assessments and monitoring of the COVID-19 situation will be conducted by the sponsor with input from the investigators. These ongoing assessments include changes to any of the following:

- Potential impact on trial participants
- Potential impact on trial site staff, including local or central IRBs
- Potential impact on sponsor/CRO staff conducting site monitoring and central review of data.

The outcome of these ongoing assessments could result in site-specific mitigation plans, which could include:

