| Electrocardiogram ⁷ | X ¹² | X | X | | | |
| Randomization/ Study drug administration | X | X | X | | | |
| Continuous telemetry ⁷ | X | X | X | | | |
| Mortality | | X | X | X | X | X |
| NIHSS ¹³ | X | X | X | X | X | X |
| mRS | X | | | X | X | X |
| Barthel Index | X | | | | X | X |
| EQ-5D-5L | | | | | | X |
| Imaging (NCCT & mCTA) | X | | | | | |
| Endovascular Procedure | X | | | | | |
| MRI head ⁸ | | X | X | | | X |
| Laboratory Assessments | X ⁹ | | X | | | |
| Pregnancy test ¹⁰ | X | | | | | |
| Blood collection for RNA analysis ¹¹ | | X | X | | | X |
| Blood collection for Plasma Biomarker | | X | X | | | X |
| AE | Collected to Day 90 | | | | | |
| SAE | Collected to Day 90 | | | | | |
| Prior medications | X | | | | | |
| Concomitant medications | | | | Collected to Day 90 | | |

1. Visit will occur at Day 6 or hospital discharge if prior to Day 6.
2. At Day 30 and Day 90 it is preferred that participants will return to clinic. If an in-clinic visit is not possible the participant can be contacted by telemedicine (preferred) or by telephone (last option).
3. If the original process involved anyone other than the participant (and if required), site staff will make ongoing efforts until: (1) regained capacity consent is obtained from participant, (2) death, or (3) completion of the Day 90 assessment.
4. Physical exam every 8-12 hours during Day 1 and Day 2.
5. At baseline estimated or actual weight will be collected. If an estimated weight was collected at baseline, actual weight should be collected as soon as feasible and prior to discharge.
6. Vital signs (Blood Pressure (BP), Heart Rate (HR) only) will be recorded immediately before and after completion of the study drug infusion, and every 8-12 hours during Day 1 and Day 2, temperature will be collected at baseline only if standard of care.
7. Abnormal electrocardiogram or continuous telemetry result that suggests clinical instability will prompt a formal cardiology consult.
8. Magnetic Resonance Imaging (MRI) head with perfusion imaging within approximately 2h post-EVT on Day 1 and at 48h +/- 4h. MRI head only at 90d.
9. Blood should be drawn at baseline, but results are not required prior to randomization. Results from primary hospital (within 8 hours) are accepted.
10. If the participant is female and is of childbearing potential a pregnancy test (urine or serum point-of-care pregnancy test) must be collected at baseline, but result is not required prior to randomization.

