11. Day 1 collection 12-24 h (+/-4 hours) after additional consent is obtained for optional collection.
12. Results from the baseline Electrocardiogram (ECG) and Chest X-ray(CXR) are not required prior to randomization.
13. NIHSS score is obtainable in-person or via telemedicine visit only (not over the phone).

D = days; h = hours

2.2.2 *Randomization and Blinding*

All subjects will be centrally assigned according to the study's Randomization and Study Product Management Plan to a randomized and blinded study intervention (i.e., RNS60 0.5 mL/kg/h, RNS60 1.0 mL/kg/h, or placebo 1.0 mL/kg/h) using block urn randomization tables (8 urns). The randomization table will be set for up to 126 subjects per urn to ensure no urn can be filled prior to enrollment completion. Each site will have its own randomization table. All subjects are identified by a 5-digit number (e.g., 01-001), consisting of a unique 2-digit site number followed by a 3-digit subject number. Each subject number is unique and will not be reused.

Treatment allocation will be assigned using 1:1:1 randomization of three arms with block urn randomization by age, NIHSS score, and ASPECTS. Randomized allocation will be fully concealed by having allocations based upon random assignment and blinded by the use of RNS60 and placebo infusion bags and labels with identical visual appearance. The lower rate of infusion associated with the low-dose RNS60 poses potential for unblinding of study staff involved with infusion administration to the low-dose group, however assessors and subjects will remain blinded. Each infusion bag will have a unique 5-digit identification number.

The purpose of using block urn randomization is to minimize the possibility of imbalance of treatment assignment by age, NIHSS score, and ASPECTS due to the small sample size. Block urn randomization provides consistent imbalance control but provides greater allocation randomness compared with permuted block design and can be used for more than three arms.

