The NIHSS is a standardized neurological examination scale that is a valid and reliable measure of disability and recovery after acute stroke. The NIHSS assessment is a standardized 15-item impairment scale, intended to evaluate neurologic outcome and degrees of recovery for subjects with stroke. The scale assesses levels of consciousness, extraocular movements, visual fields, facial muscle function, extremity strength, sensory function, coordination (ataxia), language (aphasia), speech (dysarthria), and hemi-inattention (neglect). The NIHSS will be administered at baseline, post-EVT (2h), 24h, 48h, Day 6 (or discharge), Day 30 and Day 90. The NIHSS will only be scored by those trained in the use of this scale.

Table 3. Scales and score range in NIHSS

| Item | Scales | Score range |
|------|----------------------------|-------------|
| 1a | Level of Consciousness | 0-3 |
| 1b | LOC Questions | 0-2 |
| 1c | LOC Commands | 0-2 |
| 2 | Best Gaze | 0-2 |
| 3 | Visual | 0-3 |
| 4 | Facial Palsy | 0-3 |
| 5a | Motor Arm –Left Arm | 0-4 |
| 5b | Motor Arm –Right Arm | 0-4 |
| 6a | Motor Leg –Left Leg | 0-4 |
| 6b | Motor Leg – Right Leg | 0-4 |
| 7 | Limb Ataxia | 0-2 |
| 8 | Sensory | 0-2 |
| 9 | Best Language | 0-3 |
| 10 | Dysarthria | 0-2 |
| 11 | Extinction and Inattention | 0-2 |

Scoring:

Each item is scored in the respective ranges listed in Table 3 (0-2, 0-3, or 0-4), and untestable items are scored as "UN". A score of 0 indicates normal performance. Total scores on the NIHSS range from 0-42, with higher values reflecting increasing severity.

Stroke severity is further stratified in the following way (Brott, Adams, Olinger, Marler, Barsan, Biller, & Hertzberg, 1989):

> 25: Very severe

15-24: Severe

5-14: Mild to moderately severe

< 5: Mild

The predictive value of the scale can also aid in planning a subject's rehabilitation or long-term care needs as early as on the day of admission. NIHSS scores can be

interpreted in the following way (Schlegel, D., Kolb, S. J., Luciano, J. M., Tovar, J. M., Cucchiara, B. L., Liebeskind, D. S., & Kasner S. E., 2003):

≥ 14 – Severe: Long-term care in nursing facility required

6-13 – adequate: Acute inpatient rehabilitation required

≤ 5 – Mild: 80% with this score are discharged home

4) The proportion of study subjects with worsening of stroke at the 90-day study period.

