The dataset generated in Step 3 will be imputed based on the assumption of MNAR, using Copy-Reference imputation. The MNAR imputation will be based on the placebo group, i.e. data from the placebo group only will be used to generate the imputations. For this, the MNAR statement will be used as described below.

<

KEY SENSITIVITY ANALYSIS (analysis assuming MNAR)

The analysis consists of the following steps:

1. Imputation of all intermittent missing data with MI assuming MAR, in order to generate a dataset with monotone missing data structure.
2. Based on dataset generated in Step 1: imputation of all monotone missing data with MI assuming MAR, in order to generate dataset with no missing data
3. Based on dataset generated in Step 2 (with no missing data): all visits that have monotone missing data that are not due to COVID-19 will be set back as missing for subjects in the active arms
4. Based on dataset generated in Step 3: imputation of remaining monotone missing data (not related to COVID-19) with multiple imputation assuming MNAR (Copy-Reference imputation)
5. Based on dataset generated in Step 4, analysis of imputed data with GLMs
6. Combination of results from the GLMs.

Step 1: Imputation of intermittent missing data

Multiple imputation techniques will be applied in the ITT analysis set. For subjects with intermittent missing values, a monotone missingness pattern will be generated. Intermittent missing values will be imputed using the Markov Chain Monte Carlo (MCMC) methodology which assumes a multivariate normal distribution over all variables included in the imputation model. The MI

procedure in SAS will be used for this purpose and this first MI step will be repeated 500 times, generating 500 different datasets. A random seed value will be used in the MI procedure and documented in this SAP, to allow replication of the analysis. Seed value of 2003 will be used. The imputation is based on the MAR assumption, i.e., the missing data are assumed to follow the same model as the other subjects in their respective treatment arm. Age, NIHSS, and ASPECTS are included as a factor in the model because the randomization is stratified by these factors. The following SAS code will be used to generate the missing data pattern:

[REDACTED]

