Additionally, neurological functioning at Day 90 will be examined by NIHSS scores at Day 90 between the three treatments (RNS60 1.0 mL/kg/h, RNS60 0.5 mL/kg/h, and placebo 1.0 mL/kg/h). GLM analysis and missing data imputation analysis at Day 90 will be performed using the same approach described above for neurological functioning using 24-hour NIHSS scores.

4. The proportion of subjects with worsening of stroke over the 48-hours/duration of admission:

Worsening of stroke is defined (i.e., Yes or No) as: progression, or hemorrhagic transformation, of the index stroke as documented by medical imaging and that is (a) life-threatening requiring intervention and/or (b) results in increased disability as gauged by a \geq 4-point increase from lowest NIHSS pre decline and/or (c) results in death. Subjects with worsening of stroke will be identified based on a \geq 4-point increase in their worst minus best NIHSS score and adverse events status (life threatening requiring intervention or death) as collected in the CRFs.

The simple effect of treatment on worsening stroke at 48 hours/admission duration will be examined by comparing the proportion of subjects who had worsening stroke (Yes or No) between the three treatments (RNS60 1.0 mL/kg/h, RNS60 0.5 mL/kg/h, and placebo 1.0 mL/kg/h) using GLM using residual pseudo-likelihood with a subject-specific expansion (RSPL) assuming a binary distribution. Covariates include the Age, baseline NIHSS, and baseline ASPECTS as binary factors used for block urn randomization, log of baseline infarct volume, baseline perfusion status, baseline occlusion location, and study site.

The predicted probability for each treatment group and LS mean difference between high-dose and placebo and low-dose and placebo groups along with the 95% CIs will be provided using the LSMEANS/DIFF statement. The comparison of the two combined active arms versus placebo will be performed using the LSMESTIMATE statement with the ILINK option. The odds ratio will also be calculated. The P-value for the hypothesis testing will also be provided. Treatment difference will be assessed with a 2-sided alpha level of 0.05.

The sample SAS code planned for the analysis is outlined below.

5. Barthel Index.

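### In the additional Day 90 NIHSS analysis, patients known to be alive but reached only by phone appear to be imputed from data that include the deaths' 42s, so imputed scores and arm means run too high

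*SAP*

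**What the plan says.** **Deaths.** SAP 3.1.7 assigns "6 for mRS, 42 for NIHSS and 0 for BI" at all scheduled visits after death. It adds: "The values for NIHSS and BI are conventions, consistent with the worst possible score". SAP 2.1.3 confirms that these endpoints need no imputation in patients who die.

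**Phone contacts.** Day 30 and Day 90 may be done by phone as a last resort (SAP Table 1, note 2). NIHSS needs an in-person or telemedicine visit (note 13). Protocol 13.1 states the consequence: "If the contact is made by phone, only the NIHSS assessment will not be completed, all other assessments will be obtained".

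**Day 90 NIHSS.** The SAP's ranked NIHSS endpoint is at hour 24. Day 90 is added at the end of SAP 3.4.2 (3): "GLM analysis and missing data imputation analysis at Day 90 will be performed using the same approach described above". That approach is:
- analysis on the raw score (SAP 3.4.2);
- MAR (SAP 3.1.6, which names the 24-hour score);
- for the sensitivity analysis, "Intermittent missing values will be imputed using the Markov Chain Monte Carlo (MCMC) methodology which assumes a multivariate normal distribution", with missing values taken to follow the same model as the rest of the arm, and age, NIHSS and ASPECTS as the named factors;
- a copy-reference step that refills active-arm monotone gaps not due to COVID-19 from placebo data.

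No visible text conditions on vital status or limits the donors to survivors.

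**The concern.** Take two patients with the same earlier scores. The one who has died cannot have a missing Day 90 NIHSS, because 42 is entered. The one who is alive and reached by phone always has a missing one. Missingness therefore depends on being alive, which is part of the Day 90 outcome and is not in the visible model. For this kind of missing value, MAR given earlier NIHSS fails by construction, and a patient known to be alive is given a share of the risk of death.

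The approach was written for hour 24, when patients are still in the infusion period and phone contact is not in use. Carrying it to Day 90 brings in both the accumulated deaths and the phone gaps. The copy-reference step does not help, because placebo deaths also carry 42.

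What is at stake is the Day 90 mean NIHSS and its spread by arm. The protocol synopsis lists this mean as a secondary outcome, and Protocol 9.3.3 wants effect sizes from this trial to power the next one.

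**Working it through.** **1. The plan's own figure.** "Total scores on the NIHSS range from 0-42". The item maxima in SAP Table 3 give 3+2+2+2+3+3+4+4+4+4+2+2+3+2+2 = 42, so 42 is the worst score, as stated.

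**2. Inputs.** Deaths p = 10% (SAP 2.2.4; range tried 5-20%). About 100/3 ≈ 33 patients per arm. Assumed, because the documents give no figures: survivor mean μ ≈ 5 and SD ≈ 5.5 at Day 90, phone share of survivors f = 10-40%, visit-to-visit correlation 0.8, and three splits of death timing.

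**3. Mechanism without predictors.** Filling from everyone observed in the arm gives

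fill = [42p + (1−p)(1−f)μ] / [p + (1−p)(1−f)].

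With p = 0.10, f = 0.20, μ = 5: (4.2 + 3.6)/(0.10 + 0.72) = 7.8/0.82 = 9.5, against a true 5. The arm mean becomes 9.5 against a true 0.1×42 + 0.9×5 = 8.7. A model that simply dropped missing patients would give the same arm mean. This is an upper limit, because earlier scores absorb part of the error.

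**4. With earlier NIHSS as predictors.** Simulation of 400,000 patients, normal regression on earlier scores, 10% deaths, phone contact at random among survivors. Arm-mean excess = (excess per imputed patient) × (1−p) × f.

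| Death timing | Phone | Excess, Day 30 seen | Excess, Day 30 also by phone | Arm mean excess |
|---|---|---|---|---|
| Half in the earliest interval | 10% | 1.07 | 1.92 | 0.10 / 0.17 |
| Half in the earliest interval | 20% | 1.17 | 2.07 | 0.21 / 0.37 |
| Even thirds | 10% | 1.31 | 2.30 | 0.12 / 0.21 |
| Even thirds | 20% | 1.47 | 2.54 | 0.27 / 0.46 |
| 70% in the earliest interval | 20% | 0.60 | 1.44 | 0.11 / 0.26 |

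Check of row 2: 2.07 × 0.9 × 0.2 = 0.37. At 30% phone with both visits missed, a separate run gave an arm-mean excess of 0.71. Over 5-20% deaths and 10-40% phone, the excess per imputed patient ran from 0.3 to 5.7 points and was positive in every setting. Fitting in survivors only recovered the truth (5.30-5.32 against 5.32 in row 2).

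**5. Between-arm difference (high dose minus placebo).** Ranges run over Day 30 seen or missed.

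| Deaths, placebo / high dose | Phone, placebo / high dose | True | MAR | Copy-reference |
|---|---|---|---|---|
| 10% / 10% | 30% / 30% | 0.01 | 0.01 | 0.01 |
| 10% / 5% | 30% / 30% | −1.72 | −1.86 to −1.97 | −1.62 to −1.66 |
| 10% / 10% | 20% / 40% | 0.00 | +0.30 to +0.54 | +0.20 to +0.37 |

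**6. Against the standard error.** At 10% deaths the unadjusted variance is 0.9×5.5² + 0.1×0.9×37² = 27.2 + 123.2 = 150.4, so SD = 12.3 and SE = 12.3×√(2/33) = 3.0. The largest shift in the third row is 0.54/3.0 = 0.18 SE. In the second row the variance at 5% deaths is 0.95×5.5² + 0.05×0.95×37² = 93.8, so SE = √[(150.4 + 93.8)/33] = 2.7, and the largest shift is 0.25/2.7 = 0.09 SE.

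**The case against.** **Reach.** The ranked NIHSS endpoint is at hour 24, before phone contact is offered. Other time points are declared exploratory in SAP 3.4.2. The protocol is not consistent on NIHSS timing: 24 h and Day 90 in the synopsis, discharge in Table 3-1, after randomization in 3.2.2. In any case the SAP supersedes it. This stands, and limits the point to an additional analysis.

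**What can be seen.** The primary NIHSS model text cannot be read in the version reviewed and the imputation code is blacked out. A survivor restriction or extra covariates there cannot be excluded. This stands.

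**Size.** Phone is the last option, telemedicine does yield an NIHSS, and Day 90 also schedules MRI and blood draws, so phone rates may be low. If phone patients are sicker than their history predicts, the excess shrinks, to 0.5 to 0.8 points under the strongest selection tried at 10% deaths. It did not change sign.

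**Stronger readings.** A reader might infer that the treatment comparison is biased as planned. It is not when deaths and phone rates match across arms, and no reason is given for phone rates to differ between randomized, assessor-blinded arms. A reader might also infer that scoring deaths 42 is the error. It is a declared convention for a composite score. The fault lies only in using those scores to predict NIHSS in people known to be alive.

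**Conclusion.** The concern holds for the additional Day 90 NIHSS analysis and for NIHSS at Day 30, on the visible text. With 10% deaths, a survivor mean near 5, 10-30% phone contact and deaths not concentrated early, imputed survivors are about 1 point too high if Day 30 was seen and about 2 to 2.5 points too high if Day 30 was also by phone. The arm mean is about 0.1 to 0.7 points too high. The direction is firm. The size rests on phone rates, survivor scores and death timing that the documents do not give.

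The between-arm difference is biased only if deaths or phone rates differ, and in the settings tried by less than about a fifth of its standard error. The main harm is to the arm means and spread that would inform the next trial. The ranked 24-hour NIHSS endpoint is essentially unaffected. The mRS and BI are still collected by phone, so phone contact does not create this gap for them. Missing values from withdrawal or loss to follow-up are a separate matter.

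**What to change.** In SAP 3.4.2 (3), for Day 30 and Day 90:

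1. Impute missing NIHSS in patients known to be alive at that visit from survivors' data only, adding the mRS and BI obtained at the same contact.
2. Then set known deaths to 42 and run the between-arm comparison.
3. Report, by arm, how many scores are missing because of phone contact.

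Do not clip or truncate normal draws to 0-42. About a quarter of the draws fell outside that range in simulation on all data, so the temptation is real. In skewed survivor scores with a true mean of about 4.98, however, unbounded survivor-only draws averaged 4.98, clipped draws 5.4-5.5 and truncated draws 6.0-6.4. Bounding puts upward bias back. If in-range values are wanted, use predictive mean matching among survivors.

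The cost is SAP wording and programming. No new data are needed, since vital status is collected at every visit (Protocol 8.1.7). The downside is that the Day 90 result would rest on this imputation rather than on a likelihood-only model. Patients whose vital status is unknown would stay under the existing MAR and missing-not-at-random (MNAR) rules. If the unseen code already restricts to survivors, one sentence saying so is enough.
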